9.1.4.2 Laboratory parameters

Previous studies of rhC1INH have not shown any influence of rhC1INH on laboratory parameters. Hence, we will not perform additional laboratory monitoring exceeding routine laboratory controls planned by the treating team. If laboratory findings reveal abnormal values, they will be documented and reported as an AE if deemed clinically significant by the treating team or the Investigators.

9.1.4.3 Vital signs

No study specific vital signs will be assessed. All patients will be monitored regarding blood pressure, heart rate, respiratory rate and oxygen saturation as per standard operating procedures for the treatment of COVID-19 patients.

9.1.5 Assessments in Participants Who Prematurely Stop the Study

Patients who are withdrawn from the study will remain in the trial for the purpose of follow-up and data analysis and will be followed as planned with the following exceptions:

- Patients, who withdraw consent for all study measures, will be asked to have assessments performed as appropriate for the final 4 week study visit (*i.e.* a structured telephone interview). The same approach applies for all active study participants if the trial is stopped early. Patients who withdraw consent are at liberty to refuse any or all individual components of the final assessment.
- Patients who are withdrawn because they have not received any study medication will not be followed up and will not receive a final study assessment.
- Patients who discontinue the study because of safety concerns will be followed as planned.
- Patient with a type I allergic reaction will be referred to an allergist associated with the site for further work-up.

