2.2 Institutional Review Board (IRB)

The Principal Investigator and the responsible Investigator at each site ensure that approval from an appropriately constituted IRB will be sought for the clinical study prior to commencement of the study. No changes will be made to the protocol without prior IRB approval, except where necessary to eliminate apparent immediate hazards to study participants.

Reporting duties: Written progress reports will be sent to the IRB annually, or more frequently if requested by the IRB. All Suspected Unexpected Serious Adverse Reactions (SUSARS) will be reported within 7 (leading to death and life-threatening) or 15 (others) days to the IRB.

Premature Termination of the Study

Premature study end or interruption of the study is reported within 15 days. The regular end of the study is reported to the IRB within 90 days, the final study report shall be submitted within one year after study end. Amendments are reported according to [Section 2.9](#).

Reasons for terminating the clinical study or participation of a study site may include, but are not limited to, the following:

- The incidence and severity of AEs in this or other studies indicates a potential hazard to patients.
- Patient enrollment is unsatisfactory.
- Data recording is inaccurate or incomplete.
- The Investigator of the study site shows serious and/or persistent non-compliance with the clinical study protocol (CSP), the clinical research agreement, and/or applicable regulatory guidelines while conducting the study.
- The (central) ethics committee decides to terminate or suspend approval for the clinical study or the Investigator.
- Investigator is accused of fraud (i.e., altered data, omitted data, or manufactured data).

In the event that the study is terminated prematurely, the Sponsor will provide specific guidance to study sites regarding end-of-study procedures.

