4.4 Safety Objectives

The study aims to assess the safety of rhC1INH treatment in patients admitted with COVID-19 infection and receiving SOC treatment including overall incidence of adverse and serious adverse events and their relationship to the study treatment during a 3 month follow-up period.

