8.2 Administration of Experimental and Control Interventions

8.2.1 Experimental Intervention

RhC1INH (Ruconest®) will be administered at (150 U/ml) at a 50 U/kg dose (max dose of 4200 U) as a slow intravenous injection via a peripheral or central intravenous line in approximately 5 minutes every 12 hours; for 4 days. A total of 8 doses will be administered. (The licensed dosage for rhC1INH is weight-based (50 U/kg up to 84 kg and 4200 U for a bodyweight of \geq 84 kg). This is based on the aim to at least achieve a level of 0.7 U/ml C1-INH in patients with hereditary angioedema (lower limit of normal of C1-INH activity). Simulation studies have revealed that this aim is achievable with the licensed dosing⁴⁵.

However, these simulations have also shown that C1-INH levels will be lower when using 50 U/kg compared to 4200 U in patients with a bodyweight $<$ 84kg. As for the current trial the aim is not to correct underlying *absolute* C1-INH deficiency (as in case of hereditary angioedema), but to ensure that a level of at least twice the serum concentration will be achieved in the vast majority of patients, we will use the licensed dose.

In patients with normal C1-INH levels, the chosen dose will increase plasma C1-inhibitor activities by at least 100% (4200 U) respectively. To maximize efficacy rhC1INH will be administered repeatedly over 4 days. Maximal volume of the injection is 28ml (4200 U) per administration.

Repeated administration of rhC1INH was chosen for several reasons. First, hyperinflammation caused by SARS-CoV-2 is a phenomenon that may last for several days, and hence sustained inhibition of the CS and the KK system is required. Second, the elimination half-life of rhC1INH was 2.5 hours³². Third, a decline of C1-INH activity to pre-administration levels was demonstrated within four to six hours after administration of rhC1INH at a dose of 50 U/kg⁴⁶.

Duration of exposure to rhC1INH will be approximately 4 days. Participants will be followed in hospital for at least 12 hours after the last dose and via structured telephone interviews four weeks later.

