9.1.4 Assessment of Safety Outcomes

9.1.4.1 Adverse events

Participants will be followed for adverse events and outcomes for 3 months post treatment (Day 0). Assessments will be done daily while in the hospital and via a weekly follow-up telemedicine interview or telephone call after discharge.

Adverse events and clinical course including death within 4 weeks will be assessed by a weekly telemedicine or structured telephone interview for 3 months post-treatment. If necessary, medical charts will be reviewed, discharge summaries will be reviewed, or the patients' general practitioner will be contacted regarding specific follow-up information.

Every effort will be made to contact the trial subject and obtain complete data for follow-up. Conditions that started before signing informed consent will be recorded as medical history. Conditions that started or deteriorated after signing informed consent will be documented as AE. Definition of AE and SAE will be found in Section 10.

All AEs will be assessed and documented by the Investigators according to seriousness, intensity, causal relationship with study treatment, action taken with study treatment (e.g. withdrawal), specific treatment for AE and outcome. In addition, time of onset and AE duration will be recorded. Procedures are defined in Section 10. AEs will be recorded on the respective CRF pages. Participants will be asked about any new events/complaints during the hospitalization and up to 3 months post treatment. In addition, participants are asked to report any new events including hospital admission to the study team.

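### Protocol 9.1.5 assigns active participants a 4-week closing interview if the trial stops early; the current schedule has no such visit, and the rule conflicts with the 3-month adverse-event follow-up

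*Protocol*

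**What the plan says.** Protocol 9.1.5 starts from a default: withdrawn patients stay in the trial for follow-up and analysis and "will be followed as planned with the following exceptions". The first exception concerns patients who withdraw consent for all study measures. They are asked to have "assessments performed as appropriate for the final 4 week study visit", which the protocol describes as a structured telephone interview. The same bullet then extends the rule: "The same approach applies for all active study participants if the trial is stopped early". A later bullet says that patients who discontinue because of safety concerns are followed as planned.

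Elsewhere the protocol sets a longer period. Section 4.4 defines the safety objective as adverse events and "their relationship to the study treatment during a 3 month follow-up period". Section 5.4 sets the safety outcome at 3 months. Section 6.1 describes weekly contact over 3 months and total participation of about 14 weeks, give or take 5 days. Section 9.1.4.1 says: "Participants will be asked about any new events/complaints during the hospitalization and up to 3 months post treatment". Visit 7 in section 9.2.1 is a weekly interview or call for up to 3 months.

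Four-week wording also appears in protocol 8.2.1, which describes follow-up after the last dose "via structured telephone interviews four weeks later". In the SAP it appears in the safety objective (section 4) and, combined with 3 months, in the Visit 7 labels of section 3 and Table 1. SAP 5.3 and the Table 1 footnote on follow-up state 3 months.

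**The concern.** The early-stop sentence sits inside an exception to planned follow-up. Its plain sense is that, when the trial stops early, one closing interview replaces the remaining schedule, and that interview is tied to a week-4 visit the schedule no longer contains. A site following section 9.1.5 to the letter could end its weekly adverse-event calls well before the 3 months on which the safety objective rests.

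Early termination is foreseen. Protocol 2.7 lists safety risk and early signs of benefit or harm among the sponsor's reasons, and the DSMB may recommend stopping. If the trial stopped for harm, later safety information on patients already treated would be wanted more, not less. Section 9.1.5 also sits oddly with itself: a single patient who discontinues for safety reasons keeps the full schedule, while a trial-wide stop appears to shorten it for everyone still active.

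**Working it through.** **Inputs**
- Follow-up: 3 months (protocol 4.4, 5.4, 6.1, 9.1.4.1, Visit 7), taken as 3 × 30.44 = 91.3 days, or about 13 weeks, counted from Day 0.
- Screening: up to 48 hours, so 2 days (6.1). Treatment: 4 days (6.1).
- Closing contact under 9.1.5: week 4, so 28 days.

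**Step 1. Reproduce the protocol's own duration.** The stated 14 weeks ± 5 days is 98 ± 5, or 93 to 103 days.
- Screening plus 3 months: 2 + 91.3 = 93.3 days (13.3 weeks).
- Adding the treatment days: 93.3 + 4 = 97.3 days (13.9 weeks).

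Both lie inside the window, so the stated participation matches a 3-month follow-up.

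**Step 2. Try the 4-week contact instead.**
- 2 + 28 = 30 days (4.3 weeks).
- 30 + 4 = 34 days (4.9 weeks).

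Neither comes near 93 to 103 days. The 4-week visit therefore does not belong to the present schedule. That it is left over from an earlier design is an inference, since the documents show no amendment log.

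**Step 3. Size of the gap for one participant.** 91.3 − 28 = 63.3 days, and 63.3 / 7 = 9.0 weeks. Week 4 covers 28 / 91.3 = 31% of the planned period.

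**Step 4. What each reading of 9.1.5 implies at an early stop.**

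| Reading | Not yet at week 4 | Past week 4 |
|---|---|---|
| Literal (interview at week 4, then nothing) | 13 − 4 = 9 weeks of active contact lost | No rule stated: from none, if calls continue, to whatever remained at the stop |
| The 4-week label is an old name for Visit 7 | None lost | None lost |

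**Step 5. Do other provisions restore the calls?**
- Protocol 10.1.1 and 10.1.3 follow serious events already known until they resolve or stabilize. They do not look for new events.
- Section 9.1.4.1 says "participants are asked to report any new events including hospital admission to the study team". That is passive reporting.
- Section 2.2 says that on premature termination "the Sponsor will provide specific guidance to study sites regarding end-of-study procedures". The content is left open.
- The 9.1.5 bullet on safety concerns is worded for individual patients who discontinue, not for a trial-wide stop.

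None of these clearly commits sites to the weekly contacts after an early stop.

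**The case against.** The strongest reply is that the 4-week label is only a stale name. If so, the final visit is now Visit 7, and participants would be asked for its assessments. Section 9.1.5 does not say that adverse-event calls cease, and the 3-month commitment in 9.1.4.1 has no early-stop exception. Sponsor guidance at termination is the natural place to settle the matter. Much of this stands: the milder reading is open, and it means the text is ambiguous rather than clearly defective. But section 9.1.5 does not say that it means Visit 7, and guidance that restored the calls would depart from the section as written.

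The reply is also right that the trigger is narrow. Halting enrollment alone does not invoke the sentence. Nothing in the interim-analysis text says that crossing the Pocock level ends follow-up of patients already enrolled, so the two planned looks do not show that the rule would operate.

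Clinical harm is not shown either. Treatment lasts 4 days, the half-life is about 2.5 hours, and the documents give no timing of events after week 4. What can be shown is lost contact, not a lost signal.

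A reader might infer from the SAP wording that the adverse-event tables would be cut at four weeks. The documents do not support that. SAP 5.3 and the Table 1 footnote state 3 months, and SAP section 15 ties the analysis to the visits scheduled in the protocol.

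**Conclusion.** The point holds as a minor conflict in operative text. If the trial is stopped early, section 9.1.5 taken literally falls short of the 3-month safety follow-up by about 9 of 13 weeks for a participant not yet at week 4. That figure assumes the interview takes place at week 4 with no active contact afterwards, and that the 3 months run from Day 0. For participants past week 4 the section is silent, and on the milder reading the shortfall is zero.

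It would go too far to conclude that an early stop definitely ends adverse-event ascertainment, or to give a trial-wide total of lost follow-up. Such a total would need an accrual pattern the documents do not provide, and a rule for participants past week 4 that section 9.1.5 does not state.

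The Day 7 analysis, alpha and power are unaffected. The four-week wording in protocol 8.2.1 and the SAP is editorial. The 4-week all-cause mortality outcome in protocol 5.3 is a separate endpoint and is not part of the problem.

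**What to change.** Amend protocol 9.1.5 to say that, if the trial is stopped early, active participants who have not withdrawn consent complete the planned weekly adverse-event contacts to 3 months from Day 0 (Visit 7). Confine the single final interview to participants who withdraw consent. Align section 8.5, which now says that those participants will not be followed up at all.

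As tidying only:
- In protocol 8.2.1, SAP section 3 and SAP Table 1, describe post-discharge follow-up as weekly contact for up to 3 months.
- In the SAP section 4 safety objective, replace four weeks with 3 months.
- Update the SAP's reference from protocol version 3.0 to version 4.0 in the same revision.

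The cost is a wording change in both documents and, if the trial does stop early, continued weekly calls to active participants. Those calls are already planned and fall within the stated 14-week participation.

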9.2 Procedures at Each Visit

9.2.1 Split into Subtitles by Type of Visit

Visit 1, Screening (Day -1)

Informed consent will be obtained before any study-specific tests or evaluations will be performed.

- Patients who are admitted to the hospital with confirmed SARS-CoV-2 infection will be screened. Screening will be based on routinely available data and laboratory tests with only the pregnancy test as study-specific intervention/test, if necessary, before screening of the patients. Results from prior tests that will be used for screening potentially eligible subjects will be recorded in the CRF.
- Selection of potential participants according to inclusion and exclusion criteria.
- Explanation of patient information including study purpose and signature of informed consent form
- Assessment of demographics, medical history, physical examination, and concomitant medication history
- Pregnancy test if applicable
- Eligibility check (in- and exclusion criteria)
- Study enrollment

Visit 2, Intervention period (Day 0)

- Randomization
- Assignment of the trial subject identification number
- Assessment of physical examination and concomitant medications
- Assessment of vital signs including respiratory rate.
- Assessment of WHO Ordinal Scale and need for oxygen supplementation
- Collection of blood (15ml) for analysis of ferritin, IL-6, D-Dimer, C1INH concentration, and collection of blood for the analysis of complement proteins (C3 & C4).
- Routine full blood count, coagulation and biochemistry studies will only be performed.
- Virology testing (SARS-CoV-2 PCR) on a nasopharyngeal sample if not already performed before inclusion into the study
- Following randomization, participants in the active treatment group will receive rhC1INH (150 U/ml) at a 50 U/kg dose (max dose of 4200 U) every 12 hours, as a slow intravenous injection in approximately 5 minutes. The time of dosing and the dose will be recorded.
- AEs occurring after the administration will be recorded.
- Routine laboratory tests will be performed daily during admission according to standard procedures, and should include a set of hematology, coagulation and biochemistry parameters. Additionally, blood (7ml) for analysis of ferritin, IL-6, D-Dimer, C1INH concentration will be collected at the same time point.
- Monitoring of prolonged QT intervals in severely-ill subjects receiving multiple drugs.
- Measurement of oxygenation levels.
- Monitor your heart rhythms in severely-ill subjects receiving multiple drugs
- Only in the active treatment group: Collection of blood (7ml) for analysis of C1INH levels and activity 10 (+/-5 minutes) after the first administration.

Visit 3, Intervention period (Day 1)

- Assessment of physical examination
- Administration of rhC1INH (150 U/ml) at a 50 U/kg dose (max dose of 4200 U) every 12 hours, in the active treatment group as per treatment schedule. The time of dosing and the dose will be recorded.
- Assessment of vital signs including respiratory rate.
- Assessment of WHO ordinal scale and need for oxygen supplementation

- Documentation of ICU admission and/or non-invasive or invasive ventilation
- Collection of blood (15ml) for analysis of ferritin, IL-6, D-Dimer, C1INH concentration, and collection of blood for the analysis of complement proteins (C3 & C4).
- Routine full blood count, coagulation and biochemistry studies will only be performed if results from prior tests on the same day are not available.
- Only in the active treatment group: Collection of blood (7ml) for analysis of C1INH levels and activity immediately before the first administration of rhC1INH on that day.
- Routine laboratory tests will be performed daily during admission according to standard procedures, and should include a set of hematology, coagulation and biochemistry parameters. Additionally, blood (7ml) for analysis of ferritin, IL-6, D-Dimer, C1INH concentration will be collected at the same time point.
- Monitoring of prolonged QT intervals in severely ill subjects receiving multiple drugs.
- Measurement of oxygenation levels.
- Monitor your heart rhythms in severely-ill subjects receiving multiple drugs
- Assessment of AEs and concomitant medications

Visit 4, Intervention period (Day 2)

- Assessment of physical examination
- Administration of rhC1INH (150 U/ml) at a 50 U/kg dose (max dose of 4200 U) every 12 hours in the active treatment group as per treatment schedule. The time of dosing and the dose will be recorded.
- Assessment of vital signs including respiratory rate.
- Assessment of WHO ordinal scale and need for oxygen supplementation
- Documentation of ICU admission and/or non-invasive or invasive ventilation
- Collection of blood (15ml) for analysis of ferritin, IL-6, D-Dimer, C1INH concentration, and collection of blood for the analysis of complement proteins (C3 & C4).
- Routine laboratory tests will be performed daily during admission according to standard procedures, and should include a set of hematology, coagulation and biochemistry parameters. Additionally, blood (7ml) for analysis of ferritin, IL-6, D-Dimer, C1INH concentration will be collected at the same time point.
- Monitoring of prolonged QT intervals in severely-ill subjects receiving multiple drugs.
- Measurement of oxygenation levels.
- Monitor your heart rhythms in severely-ill subjects receiving multiple drugs
- Assessment of AEs and concomitant medications

Visit 5, Intervention period (Day 3-13 during hospital admission)

- Assessment of physical examination
- Completion of treatment with rhC1INH (150 U/ml) at a 50 U/kg dose (max dose of 4200 U) every 12 hours (8 doses in total) in the active treatment group as per treatment schedule. The time of dosing and the dose will be recorded. (Treatment to be administer at Visit 5 on Day 3 ONLY)
- Assessment of vital signs including respiratory rate.
- Assessment of WHO ordinal scale and need for oxygen supplementation.
- Documentation of ICU admission and/or non-invasive or invasive ventilation
- Routine laboratory tests will be performed daily during admission according to standard procedures, and should include a set of hematology, coagulation and biochemistry parameters. Additionally, blood (7ml) for analysis of ferritin, IL-6, D-Dimer, C1INH concentration will be collected at the same time point. and collection of blood for the analysis of complement proteins (C3 & C4).
- Virological assessment (SARS-CoV-2 PCR in respiratory specimen) should be performed on day 4-7 (according to local standard).
- Monitoring of prolonged QT intervals in severely-ill subjects receiving multiple drugs.

- Measurement of oxygenation levels.
- Monitor your heart rhythms in severely-ill subjects receiving multiple drugs
- Assessment of AEs and concomitant medications

Visit 6, Follow-up (Day 14 (+/-2 days) or at discharge)

- Physical examination including body weight.
- Assessment of vital signs including respiratory rate.
- Assessment of WHO ordinal scale and need for oxygen supplementation
- Documentation of ICU admission and/or non-invasive or invasive ventilation
- Laboratory assessment including routine hematology, coagulation and biochemistry studies. Routine laboratory tests will be performed daily during admission according to standard procedures. Additional sample collection will be required in patients without routine testing on the day of discharge. Additionally, blood (7ml) for analysis of ferritin, IL-6, D-Dimer, C1INH concentration will be collected at the same time point, and collection of blood for the analysis of complement proteins (C3 & C4).
- Virological assessment (SARS-CoV-2 PCR in respiratory specimen) will be performed on day 14 (when still admitted) or at discharge.
- Monitoring of prolonged QT intervals in severely-ill subjects receiving multiple drugs.
- Measurement of oxygenation levels.
- Monitor your heart rhythms in severely-ill subjects receiving multiple drugs
- Assessment of AEs and concomitant medications

Visit 7, Follow-up (for up to 3 months, weekly telemedicine interview or telephone call)

- Assessment of adverse events, WHO ordinal scale, admission to ICU and/or mechanical ventilation by structured telemedicine interview or telephone call. If necessary, medical charts will be reviewed, discharge summaries will be obtained, or the patients' general practitioner will be contacted regarding specific follow-up information.

